Appendix C

Hypoglycemic Fear Survey

Subject ID: _____

Clinic Visit: (dd/mmm/yyyy) : _____ / _____ / _____

Visit (check one): Baseline First Trimester Second Trimester Third Trimester Post-Partum

This survey is intended to find out more about how low blood sugar makes people feel. Please answer the following questions as frankly as possible.

I. Behavior. Below is a list of things people with diabetes sometimes do in order to avoid low blood sugar. Read each item carefully. Circle one of the numbers to the right that best describes what you do during your daily routine to avoid low blood sugar.

	Never	Rarely	Sometimes	Often	Very often
1. Eat large snacks at bedtime	1	2	3	4	5
2. Avoid being alone when my sugar is likely to be low	1	2	3	4	5
3. If test urine, spill a little sugar to be on the safe side. If test blood glucose, run a little high to be on the safe side	1	2	3	4	5
4. Keep my sugar higher when I will be alone for a while	1	2	3	4	5
5. Eat something as soon as I feel the first sign of low blood sugar	1	2	3	4	5
6. Reduce my medication (insulin/pills) when I think my sugar is too low	1	2	3	4	5
7. Keep my blood sugar higher when I plan to be in a long meeting or at a party	1	2	3	4	5
8. Carry fast-acting sugar with me	1	2	3	4	5
9. Avoid a lot of exercise when I think my sugar is low	1	2	3	4	5
10. Check my sugar often when I plan to be in a long meeting or go out to a party	1	2	3	4	5

II. **Worry.** Below is a list of concerns people with diabetes sometimes have. Please read each item carefully (do not skip any). Circle one of the numbers to the right that best describes how often you worry about each item because of low blood sugar.

	Never	Rarely	Sometimes	Often	Very often
11. Not recognizing/realizing I am having a reaction	1	2	3	4	5
12. Not having food, fruit, or juice with me	1	2	3	4	5
13. Feeling dizzy or passing out in public	1	2	3	4	5
14. Having a reaction while asleep	1	2	3	4	5
15. Embarrassing myself or my friends/family in a social situation	1	2	3	4	5
16. Having a reaction while alone	1	2	3	4	5
17. Appearing stupid or drunk	1	2	3	4	5
18. Losing control	1	2	3	4	5
19. No one being around to help me during a reaction	1	2	3	4	5
20. Having a reaction while driving	1	2	3	4	5
21. Making a mistake or having an accident at work	1	2	3	4	5
22. Getting a bad evaluation at work because of something that happens when my sugar is low	1	2	3	4	5
23. Having seizures or convulsions	1	2	3	4	5
24. Difficulty thinking clearly when responsible for others (children, elderly, etc.)	1	2	3	4	5
25. Developing long-term complications from frequent low blood sugar	1	2	3	4	5
26. Feeling lightheaded or faint	1	2	3	4	5
27. Having an insulin reaction	1	2	3	4	5

Appendix D

SMBG (Self-Monitoring Blood Glucose) Questionnaire

Subject ID: _____

Clinic Visit: (dd/mmm/yyyy) : _____ / _____ / _____

Gestational Age: 8 to 12 weeks 20 to 24 weeks 32 to 36 weeks Post-Partum

DAY	DATE	TIME POINT	BLOOD GLUCOSE BEFORE MEAL (OR BEDTIME)	SHORT-ACTING INSULIN DOSE (UNITS)	BLOOD GLUCOSE 2 HOURS AFTER MEAL
1		Breakfast			
		Lunch			
		Dinner			
		Bedtime			
2		Breakfast			
		Lunch			
		Dinner			
		Bedtime			
3		Breakfast			
		Lunch			
		Dinner			
		Bedtime			
4		Breakfast			
		Lunch			
		Dinner			
		Bedtime			
5		Breakfast			
		Lunch			
		Dinner			
		Bedtime			
6		Breakfast			
		Lunch			
		Dinner			
		Bedtime			
7		Breakfast			
		Lunch			
		Dinner			
		Bedtime			

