CGM data will be analyzed for mean blood glucose values, time spent in hyperglycemic (>240, >300mg/dl) and hypoglycemic (<50, <70, <80 mg/dl) ranges and various indices of glycemic variability. Laboratory analysis for A1C will be performed at baseline, monthly thereafter during the pregnancy, and post-partum. Routine blood tests will be performed in all subjects in each trimester (see Table 1).

Primary outcomes will be:

- 1) Glucose variability as measured by glucose excursions from self-monitoring blood glucose (SMBG) data through log books and downloads as well as CGM downloads and various indices [J-index, mean amplitude of glycemic excursion (MAGE), high blood glucose index (HBGI), low blood glucose index (LBGI)] from CGM downloads.
- 2) Changes detected by the hypoglycemia fear questionnaire.

Secondary outcomes will be:

- 1) How CGM alone and CGM with Share™ usage affect A1C compared to no CGM use,
- 2) Progression of diabetes complications (retinopathy, nephropathy),
- 3) Maternal and fetal outcomes (eclampsia/pre-eclampsia, live birth rates, birth weight, neonatal hypoglycemia, and other similar measures).

Introduction:

Among the US population, 29.1 million people (9.3%) have diabetes (1). Pre-existing diabetes has to be managed very carefully throughout pregnancy to optimize maternal and fetal outcomes (2). Among women

with T1DM who are pregnant, the tools that we have to regulate maternal glucose control include multiple daily injections (MDI), continuous subcutaneous insulin infusion therapy (CSII) also known as insulin pump therapy, and for high-risk individuals continuous glucose monitoring (CGM) (2). CGM use in pregnancy has been shown to be safe, to reduce the frequency of severe hypoglycemia, and to improve A1C values (3-6). Sensor-augmented pump therapy with CGM use continuously was shown to lower A1C more than intermittent use in pregnant women with T1DM (7). However, few studies have measured changes in glucose variability that occur with CGM use during pregnancy and no studies have evaluated how tools that allow family and friends (followers) to access glucose trends affect outcomes during pregnancy.

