A total of up to 40 pregnant women will be prospectively recruited into the study. As this is an 'open-label' study whose group stratification is based on subject characteristics (willingness to wear CGM, subject possession of iPhone, iPad, or iPod touch, follower possession of iPhone, iPad, or iPod touch), we cannot predict the number of subjects per treatment arm. Based on our current pregnant population's willingness to use CGM and device usage, we anticipate that 10 subjects will be in Group 1, 20 subjects in Group 2, and 10 subjects in Group 3. We will include up to 30 additional women in Group 3 identified through a retrospective chart review who were pregnant around the time of study enrollment and before the study began.

In addition, there will one main follower for each prospectively enrolled pregnant subject (up to 40 adults) who will be asked questions once per month about knowledge of the subject's glucose trends and interventions that s/he may have done on her behalf over the last month.

What is the schedule of events for the treatment groups?

After screening, when pregnancy is confirmed subjects will be stratified to Group 1, 2, or 3. Subjects in all groups will have similar study/clinic visits for data acquisition at the screening, pregnancy visits (which occur a minimum of monthly throughout gestation), and post-partum clinic visit. All subjects will be required to test blood glucoses at least 7 times a day throughout pregnancy. All subjects will be asked to log the SMBG values 7 times a day with insulin doses for meals for 1 week every trimester of the pregnancy.

Subjects stratified to CGM wear will be provided with a Dexcom G4 CGM, transmitter, and sensors (4 per month). Subjects stratified to CGM wear who want to use their personal Dexcom G5 devices will be asked to provide Dexcom mobile usernames (if they use G5 with an iPhone) and will be provided with sensors (4

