During this visit, pregnant subjects will receive a physical exam, vitals, medical history, demographics, and concomitant medications. Laboratory tests will be performed to assess for A1C. SMBG values will be downloaded. If applicable CGM units and insulin pumps will be downloaded.

Stratification, Visit 2 (Week 1):

Subjects enrolled in the study from pre-conception will be asked to come to clinic as soon as a home pregnancy test or serum blood test confirms pregnancy, during which time routine clinical care will be provided and subjects will be stratified to 1 of 3 study arms based on subject characteristics. Subjects who did not have a pre-conception counseling visit who come to clinic for routine clinical care before 13 weeks of gestation will combine Visit 1 (screening) with Visit 2 (stratification with CGM start). A urine pregnancy test will be administered to confirm pregnancy. Per routine clinical care, we will screen for diabetic neuropathy on physical exam, thyroid disease (TSH blood draw), and kidney disease (24-hour urine protein with creatinine). These tests will be repeated once each trimester. Also per routine clinical care, women will be asked to get a dilated retinal eye exam each trimester and to provide the BDC with a copy of the provider's report of each exam.

Women stratified to Groups 1 and 2 who own a Dexcom G4 or G5 Platinum CGM® will be given 4 sensors. Women stratified to Groups 1 and 2 who do not own a Dexcom G4 or G5 Platinum CGM® will be given Dexcom G4 CGM units, transmitters, and 4 sensors. They will also receive training in the insertion of sensors and CGM use. A Dexcom G4 Platinum® CGM sensor will be inserted that day and will be worn in 7 day periods throughout the study. Although subjects will be asked to wear the device 7 days/week, satisfactory data capture rate is regarded as 5 days of successful CGM readings. The CGM data will be unblinded (real-time use) such that subjects will be able to view glucose values and trends, as well as receive alerts for low and high sensor glucose values. Women will be asked to check SMBG at least 7 times daily (fasting, before meals, 2 hours after a meals, and at bedtime) for the duration of the study.

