Visits 3 through 13 (Weeks 5 to 40):

Subjects will come to the BDC for routine clinical care at least once per month for the duration of the pregnancy (through gestational week 40, though some women deliver up to 42 weeks gestation) and for continued study participation. Per routine clinical care, we will screen for diabetic neuropathy on physical exam, thyroid disease (TSH blood draw), and kidney disease (24-hour urine protein with creatinine) at least once each trimester. Also per routine clinical care, women will be asked to get a dilated retinal eye exam each trimester and to provide the BDC with a copy of the provider's report of each exam.

Subjects in Groups 1 and 2 will receive 4 new sensors per month, but may choose to get 2 sensors twice a month instead, at study visits. Use of acetaminophen-containing medications like Tylenol® during sensor wear may affect device performance, therefore we will ask subjects to keep a log of each time these medications are used. We will ask subjects at each monthly visit whether she used acetaminophen-containing medications during the previous month and when. Followers will be administered a brief questionnaire at the beginning of every month inquiring on the frequency of low alerts, high alerts, viewing glucose trends, and actions they may have taken on behalf of the subjects because of the above (see Table 2 and *Follower Questionnaire* for details). On source documents, we will also record how often subjects required an intervention for low or high glucose values within the previous month, and the nature of the interventions. If in Group 2, we will keep source documentation about interventions resulting from a Share™ alert within the previous month.

Data on all pregnant subjects for medications, vital signs, height/weight, insulin doses, glucometer downloads, insulin pump downloads (if applicable), and CGM downloads (if applicable) will be collected at least once per month and as often as every week. All subjects will be asked to collect a 7-point profile for SMBG measurements (blood glucose measurements before meals, 2 hours after meals, and at bedtime) along with meal insulin dosing for 1 week once per trimester (see SMBG Questionnaire). A1C will be measured once per month. Subjects will be asked about updated concomitant drugs and any AEs that may have occurred. Each subject will be given a hypoglycemic fear questionnaire.

Visit 14 (Weeks 44 to 52):

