The primary endpoints are glucose variability and changes detected by hypoglycemic fear survey. We will measure indices of glucose variability (mean glucose \pm SD, % of glucose within/above/below target ranges, J Index, High Blood Glucose Index [HBGI], Low Blood Glucose Index [LBGI], Mean Amplitude of Glycemic Excursions [MAGE], CONGA_n) throughout pregnancy using the SMBG 7-point profiles for one week taken once per trimester. Hypoglycemic fear survey results will be assessed once monthly over the pregnancy. We will compare outcomes within individuals over time and between individuals of the different study arms. We will test whether outcomes differ between women using Dexcom alone and women using Dexcom with Share™ using interaction terms, and will stratify analyses if differences by group are greater than 10 mg/dL in mean glucose levels are detected. Since SMBG logs will be taken at multiple time points over the pregnancy and since CGMs will be worn continuously for the duration of each pregnancy, linear mixed models will be used to assess changes in outcome measures (GV, time spent in target below or above target) over time in each trimester of pregnancy. We will use linear mixed models to assess changes in the hypoglycemic fear survey in each month of the pregnancy. Secondary endpoints include A1C differences among study arms. Improvement in glycemic variability parameters with a possible reduction of A1C by 0.3%, measured as the difference of the mean A1C laboratory values of the arms of the study between baseline (0-3 months, first trimester), second trimester (3-6 months), and third trimester (6 to 9 months). Mixed models account for missing data, allow for an unstructured covariance matrix for repeated measures, and account for inter-subjects correlation of measurements. Secondary outcomes will be used

in the same mixed models. Differences in frequency of low alert glucose rates, high alert glucose rates, and interventions for low or high glucose values among the followers for each study arm will be analyzed with student t-tests. A p-value < 0.05 will be considered significant, and we will perform statistical analyses with SAS software (version 9.3, SAS Institute, Cary NC).

Publication Strategy:

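### The plan does not settle whether the primary glucose indices come from self-logged profiles, meter downloads or CGM, and has no check of the log against the meter; low-side indices are the most exposed

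*Combined protocol and SAP*

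**What the plan says.** - **Source in the Statistical Analysis Plan.** Mean and SD, percentages within, above and below range, J-index, HBGI, LBGI, MAGE and CONGA are measured "throughout pregnancy using the SMBG 7-point profiles for one week taken once per trimester". The same paragraph mentions continuous CGM wear when it justifies the mixed models.
- **Source in the opening summary.** The first primary outcome rests on "self-monitoring blood glucose (SMBG) data through log books and downloads as well as CGM downloads and various indices". The list of indices there (J-index, MAGE, HBGI, LBGI) ends "low blood glucose index (LBGI)] from CGM downloads".
- **Who records the profile.** In the schedule of events for the treatment groups: "All subjects will be asked to log the SMBG values 7 times a day with insulin doses for meals for 1 week every trimester". Visits 3 through 13 point to the SMBG Questionnaire for this.
- **The form.** Appendix D has columns for day, date, time point, glucose headed "BLOOD GLUCOSE BEFORE MEAL (OR BEDTIME", insulin dose, and glucose two hours after the meal. It has no field for device, clock time or verification.
- **The meter record.** Under Visits 3 through 13, "glucometer downloads, insulin pump downloads (if applicable), and CGM downloads (if applicable) will be collected at least once per month". Table 1 marks the meter download at every visit.
- **What CGM wearers see.** Under Visit 2, the sensor data are unblinded, so that "subjects will be able to view glucose values and trends, as well as receive alerts".
- **Retrospective controls.** Up to 30 are added to about 10 prospective Group 3 women. The Control Arm section takes their glucose data from the chart, including meter downloads, and says they completed none of the study questionnaires. The SMBG form is not named separately there.

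**The concern.** The Statistical Analysis Plan and the opening summary give different sources for the same primary indices, with no order of precedence. If the Statistical Analysis Plan is followed, the values are those the woman chose to record, although a device record should normally exist for the same week.

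Three kinds of error are then possible. Any prospective woman can leave out a low reading or round it. Only CGM users can enter a sensor value in place of a fingerstick, so that error would fall on Groups 1 and 2 alone. And if most of Group 3 contributes meter memory while the CGM arms contribute logs, the recording method itself differs between the groups compared.

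At stake is the hypothesis that CGM lowers the share of values below target. The indices that carry it, percentage below range and LBGI, depend on a few readings per week. A difference between arms in those indices could not be separated from a difference in what was recorded.

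**Working it through.** **The plan's own figures.** The only sample-size arithmetic is 40 × 0.20 = 8 dropouts and 40 − 8 = 32 completers. It reproduces, and this point does not depend on it. The plan gives no SD, effect size or misreporting rate for the glucose indices.

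**Weight of one reading.** 7 time points × 7 days = 49 readings; 1/49 = 2.0 percentage points. As an example, assume four readings below 70 mg/dL in a full week (70 is one of the hypoglycemia thresholds in the opening summary):
- all recorded: 4/49 = 8.2%
- two left out: 2/47 = 4.3%
- two written as 70: 2/49 = 4.1%

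**Average effect of unlogged lows.** All inputs here are assumptions: lognormal glucose limited to 30–450 mg/dL, three mean/SD pairs, 49 readings a week, 4,000 simulated weeks per scenario, each reading below 70 dropped independently with the stated probability. LBGI is the mean over all readings of 10f² where f < 0 (zero otherwise), with f = 1.509 × (ln(glucose)^1.084 − 5.381).

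| Mean/SD (mg/dL) | % <70: all logged | 25% of lows dropped | 50% dropped | LBGI: all logged | 25% dropped | 50% dropped |
|---|---|---|---|---|---|---|
| 120/40 | 6.65 | 5.12 | 3.40 | 1.71 | 1.51 | 1.29 |
| 130/50 | 6.95 | 5.25 | 3.57 | 1.69 | 1.46 | 1.22 |
| 145/60 | 5.02 | 3.87 | 2.74 | 1.26 | 1.09 | 0.93 |

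With half of the lows dropped (1.3 to 1.7 readings a week on average):
- Percentage below 70 falls by 3.25/6.65 = 49%, 3.38/6.95 = 49% and 2.28/5.02 = 45%.
- LBGI falls by 0.42/1.71 = 25%, 0.47/1.69 = 28% and 0.33/1.26 = 26%.
- Mean glucose rises by only 2.2, 2.7 and 2.4 mg/dL, and SD falls by 0.8, 0.6 and 0.6 mg/dL.

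**From one arm to a comparison.** If two arms have the same true glucose and drop lows at the same rate, the false difference is zero on average. If one arm drops half and the other none, it is 2.3 to 3.4 percentage points. If one drops a quarter and the other none, it is 6.65 − 5.12 = 1.5, 6.95 − 5.25 = 1.7 and 5.02 − 3.87 = 1.2 points. Copied sensor values are not quantified, because the documents give no sensor-versus-meter error.

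**Recording method by arm.** Anticipated Group 3: 10 prospective + up to 30 retrospective = 40; 30/40 = 75% would have chart meter downloads and probably no Appendix D form.

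**The case against.** The strongest reply is that the opening summary already names downloads, so a reader who infers that the primary indices simply are self-written numbers goes too far. That stands: it is one reading of conflicting text, and the Statistical Analysis Plan does not exclude the meter. But the summary gives no precedence, and prospective Group 3 women and the retrospective controls have no sensor, so any comparison with them needs a rule for SMBG data in any case.

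A reader might also infer that misreporting occurs. The documents show only that it could. Recording by hand is likewise an inference from the form's layout, since Data Collection Tools allows electronic surveys in general. Electronic self-entry would be no better verified. That a download covers the profile week is also inferred, from its monthly frequency.

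There are partial safeguards. The form is titled and headed for blood glucose, at least seven tests a day are required, and CGM users are trained to confirm with a fingerstick before acting. None of these governs or checks what is logged.

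Finally, omission and rounding are open to all prospective women, so they do not by themselves produce an arm difference, and this is a non-randomized pilot without formal power. Both points limit the weight of the concern. The mechanisms that do differ by arm are copied sensor values and the retrospective controls' different data source.

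**Conclusion.** The concern holds as a source conflict and a missing verification rule. It does not show that the endpoint is already biased. The exposure is concentrated in percentage below range and LBGI; mean and SD are little affected by omitted lows, so the stronger claim that all the glucose indices are materially at risk from omission is not supported. Under the assumed distributions, a false difference between arms in percentage below 70 ranges from zero (equal omission) to about 3.4 points (half of the lows unlogged in one arm only). Those figures show direction and rough size only, because both the glucose distributions and the misreporting rates are assumptions. The change is worth making before analysis: the plan already collects meter downloads, and without a rule up to three quarters of Group 3 may be measured differently from the CGM arms.

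**What to change.** 1. Reconcile the opening summary with the Statistical Analysis Plan: name one source for each index and each comparison.
2. For between-arm comparisons, take SMBG values from the meter download in all arms. This assumes that the download carries date and time, which the documents do not describe.
3. Use the Appendix D dates for prospective women. For retrospective controls, pre-specify a 7-day window in the same gestational bands as the form (8–12, 20–24 and 32–36 weeks).
4. Assign readings to the seven time points by meter clock time with a pre-specified rule, for example one reading per time window, chosen without regard to its value. Use the form only to help with meal timing; it cannot label a low that was never logged. Apply the same rule in every arm to extra readings prompted by alerts, which could otherwise make sampling differ by arm.
5. Treat a log entry with no matching meter reading as missing in the main analysis. Report log-versus-meter agreement and a sensitivity analysis with all logged values.

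No new measurement is needed. The cost is plan wording and data-management time: up to 49 × 3 = 147 readings per woman over pregnancy, or 147 × 40 = 5,880 to match for the prospective women. Some values will be missing where a second meter was not downloaded.

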Appendix E

Follower Questionnaire

Subject ID: _____

Clinic Visit: (dd/mmm/yyyy) : _____ / _____ / _____

Gestational Age of Pregnant Participant:

4 to 8 weeks 8 to 12 weeks 12 to 16 weeks 16 to 20 weeks 20 to 24 weeks

24 to 28 weeks 28 to 32 weeks 32 to 36 weeks 36 to 40 weeks 40 to 42 weeks

4 to 12 weeks post-partum

LOW GLUCOSE QUESTIONS

How many times were you alerted to low glucose levels this month?

Never 1-5x mo 1-5 x weekly Daily More than 1 x daily N/A

Did you intervene to help your pregnant partner with low glucose levels this month?

Yes No

If yes, how often?

Never 1-5x mo 1-5 x weekly Daily More than 1 x daily N/A

If yes, what was the nature of the intervention? Check all that apply.

Gave glucose tablets/gel Gave glucagon injection

Gave food or drink with carbohydrates Called health care provider

Checked blood glucose level Called emergency services (like 911)

Other (Please describe: _____)

How many times did your pregnant partner's low glucose levels interfere with her daily activities this month?

Never 1-5x mo 1-5 x weekly Daily More than 1 x daily N/A

HIGH GLUCOSE QUESTIONS

How many times were you alerted to high glucose levels this month?

Never 1-5x mo 1-5 x weekly Daily More than 1 x daily N/A

Did you intervene to help your pregnant partner with high glucose levels this month?

Yes No

If yes, how often?

Never 1-5x mo 1-5 x weekly Daily More than 1 x daily N/A

If yes, what was the nature of the intervention? Check all that apply.

Gave insulin shot Checked ketone level

Gave insulin through an insulin pump Called health care provider

Checked blood glucose level Called emergency services (like 911)

Other (Please describe: _____)

How many times did your pregnant partner's high glucose levels interfere with her daily activities this month?

Never 1-5x mo 1-5 x weekly Daily More than 1 x daily N/A

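### The Follower Questionnaire leaves its recall window undefined: the items ask about the current month, the form is given at that month's start, and the protocol intends the month before

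*Combined protocol and SAP*

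**What the plan says.** Three places in the combined protocol and SAP set the period that a follower reports on.

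- **The form (Appendix E).** It asks "How many times were you alerted to low glucose levels this month", "Did you intervene to help your pregnant partner with low glucose levels this month" and "How many times were you alerted to high glucose levels this month". The other three stem questions (intervention for high glucose, and interference with daily activities by low and by high glucose) use the same period. The frequency answers are bands: "Never 1-5x mo 1-5 x weekly Daily More than 1 x daily N/A".
- **The timing (Visits 3 through 13).** "Followers will be administered a brief questionnaire at the beginning of every month inquiring on the frequency of low alerts, high alerts".
- **The intent (How many subjects per treatment arm?).** The main follower is to be asked monthly about knowledge of glucose trends and about "interventions that s/he may have done on her behalf over the last month".

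The follower schedule of events and Table 2 say only that the form is completed monthly, on paper or through REDCap. They fix no day.

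The Statistical Analysis Plan uses the answers: "Differences in frequency of low alert glucose rates, high alert glucose rates, and interventions for low or high glucose values among the followers" are to be compared across study arms with t-tests. Secondary objective 1 concerns remote monitoring by followers that leads to interventions.

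**The concern.** A form that asks about the current month, given when that month has just begun, covers only the days elapsed so far if it is taken at its word. A form meant to look back covers about 30 days. Both answers go into the same box, and nothing recorded on the form lets an analyst tell them apart afterwards.

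At stake is the meaning of the follower-reported frequencies. If some followers answer for a few days and others for a month, the comparison between arms mixes two quantities. Infrequent events are the most exposed, and interventions by a follower may well be among them.

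**Working it through.** The documents give no rate, sample size or power for this point, so there is no figure to reproduce. The check is mainly a comparison of text.

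**Step 1. Set the sources side by side.**

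| Source | Period or timing |
|---|---|
| Appendix E, six stem questions | current month |
| Visits 3 through 13, follower form | given at the start of each month |
| Follower schedule of events; Table 2 | monthly, no day fixed |
| How many subjects per treatment arm? | look-back over the month before |
| Visits 3 through 13 and Visit 14, women's own interventions | preceding month |
| Appendix F, women's post-partum form | preceding month |

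The look-back is the convention elsewhere in the protocol. Only the follower form departs from it.

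**Step 2. Look for anything on the form that settles the window.** The header has a visit date and gestational-age boxes, most of them four weeks wide. No instruction links the questions to the ticked box, and no start or end date is printed. The window stays open.

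**Step 3. Find which answers are sensitive.** Only *1-5x mo* is a monthly count. The weekly and daily bands are rates that a short window can still estimate: a follower alerted every day can tick *Daily* on day 3. The exposed answers are *Never* against *1-5x mo*, and the two yes/no intervention items.

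**Step 4. Illustrate, on assumed inputs.** Assume events follow a Poisson process with r events per 30 days, and that the follower answers on day d for the elapsed days only. Neither r nor d is in the documents.

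Share of the period observed = d/30: day 1, 1/30 = 3%; day 3, 3/30 = 10%; day 7, 7/30 = 23%.

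Chance of no event in the window = exp(−r × d/30):

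| r per 30 days | d = 1 | d = 3 | d = 7 | full 30 days |
|---|---|---|---|---|
| 1 | 0.97 | 0.90 | 0.79 | 0.37 |
| 5 | 0.85 | 0.61 | 0.31 | 0.007 |
| 10 | 0.72 | 0.37 | 0.10 | <0.001 |

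For r = 5 and d = 3: exp(−5 × 3/30) = exp(−0.5) = 0.61. For daily events (r = 30) on day 3: exp(−3) = 0.05.

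So at 5 events per 30 days, the top of the *1-5x mo* band, a literal answer on day 3 would be *Never* or *No* about 61% of the time, against 0.7% with the full window. At daily frequency the chance is about 5%. The low end of the weekly band is not fully protected in a window of a few days: 10 per 30 days is 10 × 7/30 = 2.3 a week, and the chance of no event by day 3 is 0.37.

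**The case against.** The strongest reply is that few followers would read the form literally. The protocol body states the look-back, the gestational-age boxes suggest a reporting period of about a month, and a person who fills in the same form every month would naturally answer for the time since the last one. Followers in all arms get the same form on the same schedule. The women themselves are asked about interventions with a clear look-back, and for Group 2 the interventions that followed a Share alert are documented separately, so secondary objective 1 does not rest on this form alone. The SAP also says that outcomes will not depend on enrolling followers, and the study is an unpowered pilot.

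Most of this stands, and it limits the size of the problem. The documents do not plan to observe only a few days, and many followers may well answer as intended. But the follower does not see the protocol body, and the form carries no instruction to the same effect. The women's reports do not replace the follower answers in the comparison that the SAP specifies among followers.

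A reader might go further and scale a monthly count by days elapsed, concluding for example that a form completed on day 3 undercounts by 1 − 3/30 = 90%. The documents do not support that: the form yields ordinal bands rather than counts, three of those bands are rates, and neither the completion day nor the share of literal readers is given. Nor do they support the inference that paper and electronic forms have different windows. The follower schedule offers both modes but does not say that mode changes the timing or differs by arm.

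**Conclusion.** The mismatch is in the text and does not depend on any assumption: the form's reference period, its scheduled timing and its stated purpose do not agree. Followed as written, the plan can produce truncated or mixed recall windows in data that the SAP compares between arms.

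The amount of misclassification cannot be computed from the documents. The figures from the Poisson illustration show only which answers are vulnerable, and hold only for a literal reader at the assumed rates and days.

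A reader might also infer a bias in the effect of Share. A mechanism can be imagined: Group 2 followers receive device alerts, while followers in Groups 1 and 3 learn of events through contact with the woman, so their events could be rarer and more easily recorded as *Never*. The documents give no event rates by arm, so this is possible but not shown.

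The data serve a secondary objective for which there is another source. That makes this a correction worth making because it is cheap, and not a threat to the primary endpoints.

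**What to change.** - In all six stem questions of Appendix E, replace the reference to the current month with a fixed look-back that matches the stated intent, for example *in the past 4 weeks*. The two follow-up items on how often the follower intervened then take the same window.
- Print the start and end dates of the window on the form and in REDCap.
- Align the three body sections (How many subjects per treatment arm?; the follower schedule of events; Visits 3 through 13) with that window.
- For a follower's first form, start the window at the later of Visit 2 or 4 weeks before completion. Followers may consent up to two months after the woman's first pregnancy visit, so a window that always began at Visit 2 could be about twice the intended length. Do not divide the ordinal bands by days covered, because they are not counts.
- Flag forms already collected with the old wording, so that the analysis can identify them.

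The cost is a minor amendment to the form and to REDCap, and a change of wording partway through collection that has to be carried into the analysis. A 4-week window on a calendar-monthly form also leaves up to 31 − 28 = 3 days of a month unreported. The recall window of forms already completed cannot be recovered.
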